2.1. Primary Objective and Endpoint

The primary objective of this trial is to evaluate the safety and tolerability of the CoVac-1 vaccine, a single dose SARS-CoV-2 specific multi-peptide vaccine combined with the TLR1/2 ligand XS15 emulsified in Montanide ISA 51 VG in adults.

2.1.1. Primary Endpoint

The nature, frequency, and severity of AEs and/or SAEs associated with administration of CoVac-1:

- Solicited: ADRs/AEs occurring from the time of each injection throughout 28 days following the procedure, facilitated by use of a volunteer diary
- Unsolicited: AEs from the time of injection throughout 56 days following injection
- SAEs from the time of injection until the final study visit for each subject
- Incidence of AESIs until the final study visit for each subject

2.2. Secondary Objectives and Endpoints

Secondary objectives of this trial are to evaluate the efficacy of the CoVac-1 vaccine in terms of induction of SARS-CoV-2 specific T-cells.

2.2.1. Secondary Endpoints

- Development of a CoVac-1 specific T-cell response to at least one of the single SARS-CoV-2 T-cell epitopes included in the CoVac-1 vaccine on Visits 2, 3, 4, 5 measured by IFN- γ ELISpot ex vivo and after in vitro T-cell amplification (compared to Visit 1), this includes:
 - Cellular conversion rate (CCR) at Visits 2, 3, 4, 5 after immunization

2.3. Exploratory Objectives and Endpoints

Explorative objectives are the duration and characteristics of T-cell responses and the analysis of induction of antibody responses to single SARS-CoV-2 T-cell epitopes included in the CoVac-1 vaccine.

Protocol		
Protocol code and Short Title:	P-pVAC-SARS-CoV-2	Date/Version:08.03.2021/V1.4

2.3.1. Exploratory Endpoints

- Characteristics of T-cell response on Visits 2, 3, 4, 5 measured by ELISpot/ICS. This includes:
 - Phenotyping of SARS-CoV-2 specific T-cells (CD4, CD8 etc.) by flow cytometry
 - Characterization of cytokine profiles of SARS-CoV-2 specific T cells (TNF, IFN, IL-2, CD107a etc.) by intracellular cytokine staining
 - Recognition rate defined as percentage of peptides inducing a T cell response in one individual
 - Intensity of T cell response to a single SARS-CoV-2 T cell epitope included in the CoVac-1 vaccine
- Induction of long-term SARS-CoV-2 specific T-cell responses 3 and 6 months after peptide vaccination.
- Induction of antibodies specific to the SARS-CoV-2 T-cell epitopes included in the CoVac-1 vaccine measured by ELISA. In case of unexpected detection of CoVac-1 specific antibodies the following assays will be performed:
 - Individual neutralization antibody titers
 - Seroconversion rates
 - Calculation of geometric mean titers (GMT) for neutralizing and binding antibodies
- Biomarkers and clinical characteristics influencing immunogenicity.

Protocol		
Protocol code and Short Title:	P-pVAC-SARS-CoV-2	Date/Version:08.03.2021/V1.4

3. Study Design

This is an interventional, open-label, phase I trial evaluating the CoVac-1 vaccine, a single dose SARS-CoV-2 specific multi-peptide vaccine combined with the TLR1/2 ligand XS15 emulsified in Montanide ISA 51 VG in adults. The study is divided into two parts, which will recruit consecutively. Prior to initiation of the next part, the previous part must have completed recruiting, and day 28 of the last patient enrolled must have passed. After interim safety analysis and approval from the authorities (section 9.5), the next study part starts recruiting (Figure 1 and 2).

The first volunteer included in the trial will be hospitalized after vaccination and closely monitored. This patient is observed until day 28 and possibly arising safety issues are reported to and decided on by the Sponsor. Thereafter, no more than one subject per day will be treated/vaccinated. 28 days following vaccination of the 12th volunteer, there will be an interim analysis of safety and a safety review by the data safety monitoring board (DSMB) as well as a substantial amendment to the regulatory authorities (PEI and EC) before proceeding to Part II. Part II must not start recruiting prior to approval by authorities. Volunteers of part II are treated simultaneously. Details can be found in figure 3.

To avoid bias in treatment, a manualized process protocol as well as monitoring and treatment reports are implemented. The volunteer selection will be documented. Reasons for refusal will be assessed. To avoid bias in data analysis, monitoring and analysis by intention-to-treat are planned. Data analysis will be conducted by an independent statistician.

Figure 1: Overall Study Design

Protocol		
Protocol code and Short Title:	P-pVAC-SARS-CoV-2	Date/Version:08.03.2021/V1.4

Figure 2: Individual Study Procedure

[figure not shown]

Figure 3: Treatment sequence

3.1. Study Duration and Schedule

The duration of the trial for each subject is expected to be 6 months, including 2 months of safety follow-up after vaccination and 4 months of follow-up.

The overall duration of the trial is expected to be approximately 12 months including the preparatory phase. Recruitment of subjects will start in Q3 2020. The actual overall duration or duration of recruitment may vary. The study timeline is described in Table 2.

Table 2: Study Timelines

Total trial duration	12 months
Duration for individual volunteer	Study treatment: 2 months Follow-up: 4 months
FSI (First Subject In)	Q4/2020
LSI (Last Subject In)	Q1/2021

Protocol		
Protocol code and Short Title:	P-pVAC-SARS-CoV-2	Date/Version:08.03.2021/V1.4
LSO (Last Subject Out)	Q3/2021	
DBL (Data Base Lock)	Q3/2021	
Statistical Analyses Completed	Q4/2021	
Trial Report Completed	Q4/2021	

3.2. End of Study

The end of the study is defined as the last visit of the last volunteer.

4. Study Population

Healthy subjects (designated as volunteers):

Healthy adult women and men aged 18-55 (Part I), followed by adult women and men aged 56-80 with age adjusted health condition (Part II). Volunteers will be recruited by means of paper- and online-based calls as considered appropriate by the EC of the University Hospital of Tuebingen.

4.1. General Criteria for Subject Selection

Adult male and female volunteers fulfilling the inclusion criteria outlined below will be enrolled. The trial population will consist of both genders. Gender distribution in the trial is supposed to reflect the distribution in the population; there will be no prior defined quantitative ratio between females and males.

4.1.1. Inclusion Criteria

Subjects meeting all of the following criteria will be considered for admission to the trial:

1. Adult male or non-pregnant, non-lactating female
 1. Part I: Age 18-55 at the time of screening
 2. Part II: Age 56-80 years at the time of screening
2. Pre-existing medical condition
 1. Part I: Free of clinically significant health problems, as determined by pertinent medical history and clinical examination at study screening
 2. Part II: With or without pre-existing medical condition, not requiring change in therapy or hospitalization before enrollment
3. Ability to understand and voluntarily sign the informed consent form.
4. Ability to adhere to the study visit schedule and other protocol requirements.
5. FCBP and male volunteers with partners of childbearing potential, who are sexually active must agree to the use of two effective forms (at least one highly effective method) of contraception. This should be started from the signing of the informed consent and continue until three months after vaccination
6. Postmenopausal or evidence of non-childbearing status. For women of childbearing potential: negative urine or serum pregnancy test within 7 days prior to study treatment. Postmenopausal or evidence of non-childbearing status is defined as:

Protocol		
Protocol code and Short Title:	P-pVAC-SARS-CoV-2	Date/Version:08.03.2021/V1.4

1. Amenorrhoea for 1 year or more following cessation of exogenous hormonal treatments
2. Luteinizing hormone (LH) and Follicle stimulating hormone (FSH) levels in the post-menopausal range for women under 50
7. Be willing to minimize blood and body fluid exposure of others for 7 days after vaccination
 1. Use of effective barrier prophylaxis, such as latex condoms, during sexual intercourse
 2. Avoiding the sharing of needles, razors, or toothbrushes
 3. Avoiding open-mouth kissing
 4. Refrain from blood donation during the course of the study

4.1.2. Exclusion Criteria

Subjects presenting with any of the following criteria will not be included in the trial:

1. Pregnant or lactating females.
2. Participation in any clinical study with intake of any investigational drug interfering with the study primary endpoint
3. Any concomitant disease affecting the effect of the therapeutic vaccine or interfering with the study primary endpoint
4. Any immunosuppressive treatment except low dose corticosteroids ($\leq 10\text{mg}$ prednisolone/day)
5. Prior or current infection with SARS-CoV-2 tested serologically or by throat/nose swab (PCR)
6. History of Guillain-Barré Syndrome
7. Positive serological HIV, hepatitis B or C test. In case of positive HBsAg, volunteer must provide prove of hepatitis B vaccination, otherwise volunteer must be excluded.
8. History of relevant CNS pathology or current relevant CNS pathology (e.g. seizure, paresis, aphasia, cerebrovascular ischemia/hemorrhage, severe brain injuries, dementia, Parkinson's disease, cerebellar disease, organic brain syndrome, psychosis, coordination or movement disorder, excluding febrile seizures as child)
9. Baseline laboratory with lymphocyte count $\leq 1000/\mu\text{l}$
10. Only Part I:
 - o Acute or chronic, clinically significant psychiatric, hematologic, pulmonary, cardiovascular, or hepatic or renal functional abnormality as determined by the

Protocol		
Protocol code and Short Title:	P-pVAC-SARS-CoV-2	Date/Version:08.03.2021/V1.4

Investigator based on medical history, physical exam, and/or laboratory screening test

11. All parts of the clinical trial

- Diabetes mellitus Typ II requiring drug treatment
- Chronic lung disease requiring drug treatment
- Any chronic liver disease or unknown liver abnormalities defined as:
 - ALT and AST $\leq 2.5 \times$ ULN
 - γ -GT $\leq 2.5 \times$ ULN
- Chronic renal failure defined as GFR $< 60 \text{ ml/min}/1,73\text{m}^2$
- Serious pre-existing cardiovascular disease such as NYHA $\geq I$, coronary heart disease requiring coronary surgery or known pAVK \geq grade 2
- Sickle cell anemia
- Obesity (as defined by age adjusted body mass index)

12. Hospitalization at study inclusion

13. Administration of immunoglobulins and/or any blood products within 120 days preceding study entry or planned administration during the study period

14. History of blood donation within 30 days of enrolment or planned donations within the study period

15. Known hypersensitivity to any of the components included in the CoVac-1 vaccine

16. Pre-existing auto-immune disease except for Hashimoto thyroiditis and mild (not requiring immunosuppressive treatment) psoriasis

Protocol		
Protocol code and Short Title:	P-pVAC-SARS-CoV-2	Date/Version:08.03.2021/V1.4

5. General Information on the Investigational Medical Product (IMP)

Definition of terms

Drug substances:	Six SARS-CoV-2-derived HLA class II peptides derived and the TLR1/2 ligand XS15
Peptide cocktail:	Peptide cocktail for each study volunteer including 6 immunogenic SARS-CoV-2 peptides and the TLR1/2 ligand XS15
IMP/Drug product/peptide vaccine:	CoVac-1: Peptide cocktail emulsified in Montanide ISA 51 VG
IMP administration:	subcutaneous injection with 2ml syringe (e.g. BD Emerald) and needle (e.g. BD Eclipse Needle 27Gx1/2)

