Exclusion Criteria		
 1. Pregnant or lactating females 2. Participation in any clinical study with intake of any investigational drug interfering with the study primary endpoint including: 
 ○ Active infection ○ Psychiatric disorders ○ Known systemic anaphylaxis 3. Any concomitant disease affecting the effect of the therapeutic vaccine or interfering with the study primary endpoint 4. Any immunosuppressive treatment except low dose corticosteroids (equivalent to ≤ 10mg prednisolone/day) 5. Prior or current infection with SARS-CoV-2 tested serologically or by throat/nose swab (PCR) 6. History of Guillain-Barré syndrome 7. Positive serological HIV, hepatitis B or C test. In case of positive HBsAg, volunteer must provide proof of hepatitis B vaccination, otherwise volunteer must be excluded. 8. History of relevant CNS pathology or current relevant CNS pathology (e.g. seizure, paresis, aphasia, cerebrovascular ischemia/haemorrhage, severe brain injuries, dementia, Parkinson's disease, cerebellar disease, organic brain syndrome, psychosis, coordination or movement disorder, excluding febrile seizures as child)

Protocol		
Protocol code and Short Title:	P-pVAC-SARS-CoV-2	Date/Version:08.03.2021/V1.4

	
9. Baseline laboratory with lymphocyte count $\leq 1000/\mu\text{l}$
 
10. Only Part I
 
 ○ Acute or chronic, clinically significant psychiatric, hematologic, pulmonary, cardiovascular, or hepatic or renal functional abnormality as determined by the Investigator based on medical history, physical exam, and/or laboratory screening test

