13. Blood chemistry and coagulation (local lab): Alkaline phosphatase (AP), total bilirubin, aspartate transaminase (AST/ SGOT), alanine transaminase (ALT/ SGPT), lactate dehydrogenase (LDH), and uric acid, C-reactive protein (CRP), sodium, potassium, calcium, blood urea nitrogen, creatinine, glucose: at baseline and during vaccination phase, thereafter at each visit using individual institutional guidelines and the best clinical judgment of the responsible physician, which can involve more frequent testing. Prothrombin time, aPTT, and fibrinogen will be measured at baseline and at investigator's discretion during treatment.
14. Immunoglobulin/immunophenotype: Assessment of IgA, IgG and IgM; lymphocyte subsets: T (CD4⁺ and CD8⁺) as well as B and NK cells.
15. Urine analysis (local lab): pH, glucose, proteins (qualitative, dipstick accepted): at baseline and at investigator's discretion during treatment
16. HBV, HCV and HIV-1: at baseline and thereafter at investigator's discretion
17. Pregnancy testing: For all FCBP, pregnancy testing has to be performed at the screening visit. Negative results must be available prior to vaccination.
18. SARS-CoV-2 testing: Volunteer must be tested for prior or current SARS-CoV-2 infection. Patients should be tested by serological test and throat/nose swab. If screening takes more than 48 hours, throat/nose swab for SARS-CoV-2 infection must be repeated. The vaccine can only be applied if a negative SARS-CoV-2 PCR test is available on the day of vaccination not older than 48 hours. If patients develop SARS-CoV-2 typical symptoms until vaccination, testing should be repeated.
19. Vaccine CoVac-1: Peptide vaccination should be started as soon as possible after the screening visit. Peptide vaccination will be performed once.
20. T-cell response: 60 ml of heparin blood for immunomonitoring and analysis of peptide specific T-cell response will be analyzed by the [name] lab, KKE Translational Immunologie at the Department of Immunology, Tuebingen (central laboratory). Blood will be taken before peptide vaccination on V1, and during vaccination phase and follow-up at each visit.
21. Serological response: 10 ml of serum for analysis of serological response will be analysed by the Immunopathological Laboratory, University Hospital Tuebingen (central laboratory). Blood will be taken before peptide vaccination on V1, and during vaccination phase and follow-up at each visit.

1. Introduction

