6.1. Study Entry

6.1.1. *Volunteer's Informed Consent*

Subjects are informed both in writing and verbally by the investigator before any study-specific procedure is performed. Each volunteer will be informed about the modalities of the clinical study in accordance with the provided volunteer information. The volunteer is given sufficient time (≥ 24 h) to consider participation in the clinical trial and to ask for additional advise if needed. Informed consent from the volunteer will be obtained using a form approved by the responsible EC. The volunteer and informing investigator must each personally date and sign the informed consent form containing an integrated declaration on data privacy protection. The original signed document will be part of the investigator's site file and retained with it, a copy including the insurance policy of the trial will be handed to the volunteer. The informed consent process is documented in the volunteer records.

6.1.2. *Screening*

Screening will be performed within *one week* (7 days) prior to the administration of the CoVac-1 vaccine. After having signed the informed consent form, volunteers will undergo all assessments listed below:

- Demographics
- Medical history
- Enrolment
- Vital signs
- Physical examination
- Concomitant medications
- Hematology (local lab)
- Blood chemistry and coagulation (local lab)
- Urine analysis (local lab)
- Immunoglobulins/Immunophenotype (local lab), approximately 10 ml blood
- Testing for previous or current SARS-CoV-2 infection: 5ml serum blood will be drawn for antibody testing and a nose/throat swab* will be performed.
- HBV, HCV, HIV-1, (local lab)

Protocol		
Protocol code and Short Title:	P-pVAC-SARS-CoV-2	Date/Version:08.03.2021/V1.4

- Pregnancy test

* If screening takes more than 48 hours, throat/nose swab for SARS-CoV-2 infection must be repeated. The vaccine can only be applied if a negative SARS-CoV-2 PCR test is available on the day of vaccination not older than 48 hours.

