The investigator will review all information obtained from the screening procedures via an eligibility form. The investigator will confirm, in writing, whether the subject fulfils all criteria for eligibility. Volunteers who fulfil all the inclusion criteria and none of the exclusion criteria will be eligible to participate in the trial. Screening failures, i.e. screened volunteers not in compliance with all criteria, are to be excluded and the reason will be recorded in the volunteer records. Information of volunteer's trial participation can be provided to the volunteer's general practitioner if the volunteer agrees.

6.1.3. *Enrolment*

A volunteer is considered for screening when he or she has signed the Informed Consent form.

In case of confirmation of volunteer's eligibility (volunteers must meet all inclusion criteria and must not meet any exclusion criteria), volunteer will be registered under a specific Vol. ID on a subjects log kept at the trial site. Only these volunteers are enrolled in the study, all others are assessed as screening failures.

The study is open-label.

6.1.4. *Randomisation*

No randomisation will be done in this clinical trial.

6.1.5. *Concomitant Medication and Treatments*

Relevant additional medications and treatments administered to the subjects on entry to the trial or at any time during the trial are regarded as concomitant medications and treatments and must be documented on the appropriate pages of the CRF.

6.1.6. *Permitted Prior and Concomitant Medications and Treatments*

The following concomitant medications and treatments are permitted during the trial.

Part I: No concomitant medication, apart from contraception for FCBP.

Part II : Any concomitant medication (already applied at screening) for e.g. other diseases are allowed except for medications stated in section 6.1.7.

6.1.7. *Prohibited Prior and Concomitant Medications and Treatments*

The following concomitant medications and treatments are prohibited during the trial:

Protocol		
Protocol code and Short Title:	P-pVAC-SARS-CoV-2	Date/Version:08.03.2021/V1.4

- Immunosuppressive agents apart from (≤ 10 mg prednisolone or equivalent)
- During the trial, other vaccinations or non-urgent medical interventions are prohibited. Initiation of new medications, regardless of indication must be discussed with the investigator and must be noted on the participant's record.

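### Exclusion criterion 7 ties its hepatitis B vaccination exception to HBsAg, the marker of infection, and the protocol does not say which HBV markers are tested

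*Supplement*

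**What the plan says.** Criterion 7 in section 4.1.2 has two sentences. The first excludes volunteers with a "Positive serological HIV, hepatitis B or C test". The second reads: "In case of positive HBsAg, volunteer must provide prove of hepatitis B vaccination, otherwise volunteer must be excluded". The synopsis has the same rule with the same marker: "In case of positive HBsAg, volunteer must provide proof of hepatitis B vaccination, otherwise volunteer must be excluded".

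The screening entries do not say what is measured. Table 1 has a single row for HBV, HCV and HIV-1. Its footnote 16 begins "HBV, HCV and HIV-1: at baseline and thereafter at investigator" and leaves later testing to discretion. The list in section 6.1.2 has "HBV, HCV, HIV-1, (local lab" and nothing further. V1.4 nowhere mentions antibody to the surface or core antigen.

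Section 6.1.3 makes the wording decisive for enrolment: "volunteers must meet all inclusion criteria and must not meet any exclusion criteria".

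**The concern.** The exception is meant to spare volunteers whose hepatitis B result is explained by vaccination, but it is attached to a result that vaccination does not normally explain. HBsAg is the surface antigen of the virus; what vaccination leaves behind is antibody to it. This is general laboratory knowledge, since the protocol does not define the term. A site following the text could pass an HBsAg-positive volunteer on the strength of a vaccination card, and could turn away a volunteer whose only positive result is vaccine antibody.

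At stake is the interpretability of a small first-in-human safety trial. There are 36 volunteers, ALT and AST are safety parameters (section 6.4.1), and one SAE associated with CoVac-1 reaches the formal stopping rule (sections 8.2 and 8.6). A hepatic event in a volunteer with unrecognised or waived hepatitis B infection would be hard to attribute. In the other direction, suitable volunteers might be lost at screening.

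**Working it through.** The protocol gives no figure to reproduce. The check is a case reading of criterion 7, followed by a search for any passage that corrects it.

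**How the two sentences relate.** If the first sentence alone decided, every positive hepatitis B test, HBsAg included, would exclude, and the second sentence would do nothing. The second sentence therefore works as an exception, and HBsAg is the only marker it names.

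**Outcomes under criterion 7 as printed**

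| Volunteer | First sentence | Exception | Result under criterion 7 |
|---|---|---|---|
| HBsAg positive, proof of vaccination | positive hepatitis B test | applies | not excluded |
| HBsAg positive, no proof | positive hepatitis B test | not met | excluded |
| HBsAg negative, positive only for vaccine antibody | positive hepatitis B test, if that antibody is in the panel | does not apply | can be excluded |
| All markers negative | no positive test | not needed | not excluded |

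Rows 1 and 3 are the faulty ones. Row 3 depends on the panel, which the documents leave open.

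**Does anything else in V1.4 catch these cases?**

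- The synopsis repeats the same marker, so this is not a slip in one place.
- Table 1, footnote 16 and section 6.1.2 name no marker.
- Criterion 11, in all parts, excludes "Any chronic liver disease or unknown liver abnormalities defined as" certain ALT, AST and γ-GT limits. It does not mention hepatitis B markers, so it may or may not identify an HBsAg-positive volunteer.
- Criterion 3 (a concomitant disease that affects the vaccine's effect or the primary endpoint) could be applied, but it names no marker and rests on judgement.
- Criterion 10 (hepatic abnormality as judged by the investigator) is limited to Part I. Part II accepts volunteers with pre-existing conditions under inclusion criterion 2.
- Active infection appears only in the synopsis, as a sub-item of the criterion on participation in other studies. Section 4.1.2 does not carry it.

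For row 1, other criteria may still exclude, but none is certain to. For row 3, nothing supplies an exception.

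**Size.** The documents give neither HBsAg prevalence nor the share of carriers with a vaccination record. For Part II, before the other criteria are applied:

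expected number in row 1 = 24 × p × f

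where p is HBsAg prevalence among those screened and f is the share of carriers holding proof of vaccination. Both are assumptions:

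- p = 0.003 to 0.01, ignoring f: 24 × 0.003 = 0.07 to 24 × 0.01 = 0.24. This counts all carriers, so it is a ceiling for that range of p.
- The same p with f = 0.10, for illustration: 0.072 × 0.10 = 0.007 to 0.24 × 0.10 = 0.024.

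These figures show only that the expected number is well below one under such assumptions. No figure can be given for row 3, because it is zero if the panel does not include vaccine antibody.

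**The case against.** Much can be said for a narrow view of the consequences, and most of it stands.

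- A reader might infer that the criterion defeats its own purpose and lets carriers in. It does not: HBsAg-positive volunteers without proof of vaccination remain excluded, as do those positive for HIV or hepatitis C. Only HBsAg-positive volunteers with proof pass, and only this one criterion.
- A reader might infer that the exception overrides criterion 11. Exclusion criteria are cumulative, so passing criterion 7 waives nothing else, and the investigator must confirm eligibility in writing (section 6.1.2).
- A reader might infer that one admitted carrier would stop the trial. Sections 8.2 and 8.6 require an SAE associated with CoVac-1. Nor do laboratory changes count automatically: under section 6.4.2, grade 1–2 abnormalities are AEs only with symptoms or a change in concomitant therapy.
- A reader might infer that a large share of vaccinated volunteers would be turned away. That needs both a vaccination rate and a panel that the documents do not give.
- The authors may have had in mind brief HBsAg positivity just after vaccination. The text sets no time window and does not say so; proof of vaccination at any time satisfies it.

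These points limit the consequences. They do not change the marker to which the exception is attached, and no passage corrects it.

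**Conclusion.** Criterion 7 is wrong as written: its only vaccination exception is attached to the infection antigen, in both section 4.1.2 and the synopsis, and the screening entries do not say which HBV markers count. An HBsAg-positive volunteer with a vaccination record is therefore not excluded by criterion 7, though another criterion may exclude that person. A volunteer positive only for vaccine antibody can be excluded if that antibody is tested.

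The likely number affected is small and not derivable from the documents. The point does not touch the hypothesis, sample size, power or analysis. It rests on the general meaning of HBsAg and on reading the second sentence as an exception. It should be fixed before Part II screening because it decides eligibility and is cheap to mend.

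**What to change.** By amendment, before Part II screening, the sponsor should bring criterion 7 in section 4.1.2 and in the synopsis into line with the HBV entries in Table 1, footnote 16 and section 6.1.2. The reconciled text should:

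- name the hepatitis B markers tested at screening;
- state, for each marker, whether a positive result excludes, including antibody positivity without proof of vaccination and positivity for core antibody if that is tested;
- attach the vaccination exception to the marker that vaccination explains, not to the infection antigen.

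The choice of markers and of excluding results is for the sponsor and its clinical advisers. A replacement that simply swaps one marker name would leave the other results undefined and could narrow the present exclusion without saying so.

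The HBV results of the 12 Part I volunteers should then be checked against the reconciled wording and any discrepancy documented.

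The cost is a few lines of text and a look at 12 existing results. The sample size does not change. Whether any test must be added depends on what the local laboratory already runs, which the documents do not state.
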